#### **4.4 Subject Completion/ Withdrawal procedures**

The study staff will inform the subject when his/her participation has come to an end and will document the discussion in the study record. If the infant is transferred to an outside hospital prior to discharge home, then the parents will be asked to complete the parent measures (PROMIS, CESD, EPDS, PSOC) at that time instead of hospital discharge. If the parent chooses to withdraw their infant for any reason, the parent does not have to complete the above measures.

An infant may no longer participate in the study under any of the following circumstances:

- The medical condition of the infant deteriorates and the medical team no longer recommends PT or massage
- The infant experiences a severe AE or SAE related to the intervention
- The Parent is no longer interested in participating

In the event that an infant has an AE related to massage medium (Aquaphor), then massage will be performed without the medium once the skin has healed.

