#### **Screening/Baseline:**

[figure not shown]
The recruitment process with the parents will be initiated once the physical therapy referral has been made by the treating physician. The neonatology provider team will receive an introduction to the study from the PI ([name]) and chief neonatologist/grant mentor ([name]) prior to study initiation. All infants who meet eligibility criteria for the study also receive standard physical therapy orders in the Newborn Critical Care Center (NCCC). A physical therapist attends weekly developmental rounds in the NCCC and participates in the physical therapy referral process by screening patients who are under a certain age and weight. The physical therapy referral is received when the infant is clinically stable and thus should avoid the initial parent distress and need for orientation after the birth and admission to the NCCC. Once a PT referral is received for an infant born at  $<28$  weeks gestation, the PI will be notified by the receiving therapist and an IRB-approved member of the study team will approach the biologic mother and/or father of the infant to discuss the study. In order to ensure that parents have sufficient time to consider participation, the study team member will contact the family at the bedside or by phone call once the physical therapy referral has been initiated to introduce the TEMPO study. The study team member will offer to leave the consent document with the parent(s). An IRB-approved member of the study team will always be available to answer any questions related to the informed consent, and if they express interested in participating, then informed consent will be obtained.

**Intervention/Treatment and Follow up:** Please see Table 1 and Figure 1 below for information regarding the timing and sequence of intervention and follow up. Additional detail regarding the study intervention can be found in sections 4 and 7.

Table 1: Study Events

Event	Baseline	During Hospital Admission	Hospital Discharge	Post discharge	First F/U visit	F/U at 12 mos visit
Parent measures: (AIM, FIM, PROMIS, CESD, EPDS, PSOC)	x		x		x	x
PAQ						x
Parent Interview					x	x
Parent Education Sessions	x	x	x			
Salivary cortisol pre and post massage		x				
Weekly Parent Education including massage		x				
Email					bi-weekly	
Massage Review					x	
Infant measures					x	x

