#### *During infant hospitalization*

- **Visit 1: Early Parent Education Session:** Initiated within 3 weeks of infant birth. The PT will educate the parent about the importance of infant positioning, the impact of prematurity on the motor and sensory systems, and how to read and respond to infant behavioral-motor cues using a written pamphlet with pictures to supplement the verbal education lasting about 30 minutes.
  - At this visit, the therapist will have the parent fill out the following questionnaires for baseline measurement: AIM, FIM, PROMIS, CESD, EPDS, PSOC
  - The therapist will also ask the parent to complete a contact information form and a demographic form.
- **Visits 2-8: Weekly Parent Education Sessions <34 weeks:** Following the initial parent education session, the PT will hold weekly parent education sessions, ideally at the time of therapy. When the infant is this young (<34 weeks gestation), PT intervention and education will focus on infant behavioral-motor cues, reading/response to infant cues, positioning strategies/concerns, and developmentally appropriate stimulation of the infant. If the parent is not available for all therapy sessions, then the parent will receive a weekly update about their infant's progress face-to-face and/or via video chat.
  - Parents will be asked to record the frequency of physical therapy interventions on a bedside card.
- **Visits 9-10: Infant Massage Parent Education Sessions:** Parent-administered infant massage will be incorporated into the therapy plan of care as soon as the infant's medical provider determines that the infant is physiologically stable and can tolerate massage. This time is generally once the infant is approximately 34 weeks gestational age, approximately 1500 grams, and is demonstrating temperature stability out of the isolette for short periods. At a minimum, the therapist will teach massage for the back or lower extremities over 2 parent education sessions. The therapist will demonstrate massage strokes on a doll using verbal cues to guide the parent while the parent administers massage on the infant. An instructional massage pamphlet will be provided. Once the therapist has determined parent safety with massage administration, parents will be encouraged to practice infant massage when they visit the baby and to note when they do this by marking a card at the bedside.

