- Pre and Post both massage sessions, the PI or study coordinator will collect salivary cortisol via buccal swab as a measure of physiologic stress.
- **Visits 11+: Weekly Parent Education Sessions >34 weeks:** Weekly parent education once the infant is >34 weeks will begin to incorporate hands-on developmental play activities, introduction to visual engagement, and postural control practice in variety of positions that the infant tolerates. Additionally, the PT and parent may choose to review massage at these visits. If the parent is not available for all therapy sessions, then the parent will receive a weekly update about their infant's progress face-to-face and/or via video chat.
  - Parents will be asked to record the frequency of physical therapy interventions on a bedside card.
- **Final Visit during hospitalization:** Within the week of hospital discharge, the PT will schedule a face-to-face parent education session lasting about 30 minutes to review age-appropriate developmental play activities for home and review infant massage. A supplemental handout and therapist email and pager information will be provided.
  - At this visit, the therapist will have the parent fill out the following questionnaires for ongoing measurement: AIM, FIM, PROMIS, CESD, EPDS, PSOC (Aim 1).

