#### 4.3 Follow- up procedures (by visits)

The TEMPO program has additional components that extend beyond the hospital period. Parent and infant outcome measures will be collected at the first follow-up and 12 month corrected age follow-up clinic visits. Please see Table 1: Study Events and Figure 1: Study Scheme in the Appendix for a complete timeline.

After hospitalization:

- **Visit 1: Parent Education Post-Discharge:** The PT will call the parent within 2 weeks of discharge to follow up about discharge education and massage. During this phone call, the PT will review the home program and massage techniques. The PT will also answer any parent questions. Therapist email and pager information will be provided.
- **Visits 2-12 (approximate): Bi-weekly emails:** The PT will send bi-weekly emails with developmental play activity and massage reminders and tips from hospital discharge through the first follow up appointment.
  - These emails will include a link for parents to report frequency of PT intervention and massage at home.
- **Visit 13 (approximate): First Visit Follow-up Massage Review Session:** At the infant's first follow-up appointment with the multidisciplinary neonatology team, the PT will provide a gross motor screening assessment and education. In addition, as part of the TEMPO program, a PT will facilitate a parent-administered infant massage session to provide an opportunity for parent to receive feedback on technique from the PT. This session will address any safety concerns, infant changes, and parent questions.
  - At this visit, the therapist will have the parent fill out the following questionnaires for ongoing measurement: AIM, FIM, PROMIS, CESD, EPDS, PSOC
  - At this visit, the PI or study coordinator will interview the parent about acceptability of the TEMPO program.
- **Visits 14+ (approximate): Bi-weekly emails:** The PT will continue to send bi-weekly emails with developmental play activity and massage reminders until the 12 month follow up appointment.
  - These emails will include a link for parents to report frequency of PT intervention and massage at home.
- **12 Month Follow-up Appointment:** At the standard of care 12 month corrected age follow-up appointment with the multidisciplinary neonatology team, the PT will administer a standardized assessment of gross and fine motor skills (Bayley Scales of Infant Development-III).

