  - At this visit, the therapist will have the parent fill out the following questionnaires for ongoing measurement: AIM, FIM, PROMIS, CESD, EPDS, PSOC (Aim 1)

- Additionally, the parent will complete the PAQ questionnaire. (Aim 1)
- At this visit, the PI or study coordinator will interview the parent about acceptability of the TEMPO program. (Aim 1, Aim 2)

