## 6 STATISTICAL CONSIDERATIONS

### 6.1 Primary Objectives

No hypothesis tests will be performed in this study. The primary goal of this project is to test feasibility and acceptability of the TEMPO program and study protocol (Aim 1). As such, the analysis plan will not focus on inferential statistics but on measures of feasibility identified in the NCCIH's *Framework for Developing and Testing Mind and Body Interventions* (<https://nccih.nih.gov/grants/mindbody/framework>):

- Recruitment: Percentage of eligible infant-parent dyads who enroll in the study (Goal  $\geq 55\%$ )
- Willingness to be randomized: Percentage of enrolled parents who, in interviews, report they would agree to be randomized (Goal  $\geq 70\%$ )
- TEMPO delivered per protocol: Percentage of enrolled parents who complete all TEMPO components per protocol (Goal  $\geq 70\%$ ) and weekly and bi-weekly reporting of physical therapy interventions (goal  $\geq 50\%$ ).
- Retention: Percentage of enrolled parents who are retained in the study at 12 months (Goal  $\geq 70\%$ ), reasons for attrition for those who do not complete the protocol
- Complete data collection: Percentage of enrolled parents who complete data collection, including interviews (Goal  $\geq 70\%$ )
- Adherence: Percentage of enrolled parents who complete at least 2-3x/week during hospitalization and 2-3x/week in-home PTIs as noted on the parent log or survey (Goal  $\geq 70\%$ )
- Acceptability and Feasibility of TEMPO: Percentage of parents who rate acceptability and feasibility as 4/5 or 5/5 using the Acceptability of Intervention Measure and the Feasibility of Intervention Measure (Goal  $\geq 70\%$ )
- Acceptability of the Protocol: A structured interview guide will be followed by the PI or research coordinator. Interviews will be audio recorded and transcribed by a confidential online service. All audio files will be stored and transmitted using TLS 1.2 encryption for a high level of security. Interviews will be coded by the PI for content and qualitative analysis to derive themes. (Aim 1 and 2)

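### The transfer assessment in section 4.4 omits AIM and FIM, so an acceptability and feasibility result taken at hospital discharge would leave out transferred families

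*Combined protocol and SAP*

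**What the plan says.** Table 1 in section 3.1 groups six questionnaires in one row, "Parent measures: (AIM, FIM, PROMIS, CESD, EPDS, PSOC", and schedules them at baseline, hospital discharge, first follow-up and 12 months. The visit descriptions agree. At Visit 1 the parent completes "the following questionnaires for baseline measurement: AIM, FIM, PROMIS, CESD, EPDS, PSOC". At the final hospital visit (section 4.2) the parent completes "the following questionnaires for ongoing measurement: AIM, FIM, PROMIS, CESD, EPDS, PSOC", and that list is tagged to Aim 1. Section 4.3 repeats the six instruments at the first follow-up visit ("the therapist will have the parent fill out the following questionnaires for ongoing measurement: AIM, FIM, PROMIS, CESD, EPDS, PSOC") and at 12 months ("ongoing measurement: AIM, FIM, PROMIS, CESD, EPDS, PSOC (Aim 1").

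Section 4.4 sets a separate rule for infants transferred to an outside hospital before going home. Their parents are asked to "complete the parent measures (PROMIS, CESD, EPDS, PSOC) at that time instead of hospital discharge". AIM and FIM are not in that list.

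Among the primary-objective criteria, section 6.1 has "Percentage of parents who rate acceptability and feasibility as 4/5 or 5/5 using the Acceptability of Intervention Measure and the Feasibility of Intervention Measure", with a goal of at least 70%. It does not say which administration the goal is judged on.

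**The concern.** AIM and FIM are the only instruments behind the section 6.1 rating goal, and acceptability is part of the stated aim of the study (sections 2 and 6.1). The transfer assessment stands in for the discharge assessment, but it drops these two instruments and keeps the other four. A transferred parent who remains in the study and complies fully would have no AIM/FIM score between Visit 1 and the first follow-up visit.

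At stake is the completeness of any AIM/FIM result reported at discharge. Such a result would describe only families whose infant went home from this unit. The report would have no score taken at the end of the hospital phase with which to check whether transferred families rated the programme differently.

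**Working it through.** **1. The lists side by side**

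| Assessment | Section | AIM, FIM | PROMIS, CESD, EPDS, PSOC |
|---|---|---|---|
| Visit 1 | 4.2, Table 1 | yes | yes |
| Hospital discharge | 4.2, Table 1 | yes | yes |
| Transfer, replacing discharge | 4.4 | **no** | yes |
| First follow-up | 4.3, Table 1 | yes | yes |
| 12 months | 4.3, Table 1 | yes | yes |

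Only the transfer row differs.

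**2. The plan's own figure.** Section 3.2 expects about 57 eligible infants and aims to enrol 55% of dyads: 57 × 0.55 = 31.35, consistent with the stated 30. It allows up to 40.

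**3. Size of the gap.** Let N be the dyads enrolled, m those transferred without AIM/FIM, and k the favourable ratings among the N − m who give a discharge rating. Everyone else is taken to respond. The percentage over all enrolled dyads then lies between k/N and (k + m)/N, an interval of width m/N. Reaching 70% needs 21 of 30 or 28 of 40. Whether 70% is reached is undetermined when k is below that number but k + m is not. The documents give no transfer rate, so 10% and 20% are assumptions.

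| N | m | Width m/N | k for which 70% is undetermined | As % of raters |
|---|---|---|---|---|
| 30 | 3 | 10 points | 18 to 20 of 27 | 66.7% to 74.1% |
| 30 | 6 | 20 points | 15 to 20 of 24 | 62.5% to 83.3% |
| 40 | 4 | 10 points | 24 to 27 of 36 | 66.7% to 75.0% |
| 40 | 8 | 20 points | 20 to 27 of 32 | 62.5% to 84.4% |

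**4. Two examples at N = 30**

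- It does not matter: with m = 3 and 22/27 = 81.5% favourable, the bounds are 22/30 = 73.3% and 25/30 = 83.3%. Both exceed 70%.
- It matters: with m = 6 and 19/24 = 79.2% favourable, the bounds are 19/30 = 63.3% and 25/30 = 83.3%. They straddle 70%.

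**5. Precision.** The exact (Clopper-Pearson) 95% confidence interval is 50.6% to 85.3% for 21/30 and 48.9% to 87.4% for 17/24. The interval widens only slightly, so the main loss is coverage of a subgroup.

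**The case against.** The strongest reply is that the harm is conditional. Section 6.1 does not tie the goal to discharge. If it is judged at first follow-up or at 12 months, the omission in 4.4 has no effect on it. This stands, and it limits the point to a discharge-point result. Such a result is still plausible, since section 4.2 tags the discharge questionnaires to Aim 1.

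The omission may also be a slip, or it may be intended. Section 4.4 uses the same label, parent measures, as the Table 1 row that includes AIM and FIM. Against that, its four instruments all appear in the section 6.2 list for planning a later trial, which also leaves out AIM and FIM, and the summary of changes describes the additions with an and/or. The documents do not settle this. Staff following the explicit list in 4.4 would not collect the two measures.

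The bounds assume that all transferred families rate favourably or that none do. They are the extremes, not a forecast.

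A reader might infer that the views of transferred families are lost altogether. The documents do not support that: AIM and FIM recur at both follow-up visits, and the interviews at those visits (section 5) cover programme materials and components. Nor do the documents say how TEMPO runs after a transfer, so there is no basis for assuming that these families had a different experience.

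A reader might also infer that a Visit 1 rating could be used to meet the goal. Section 6.1 does not exclude it, but section 4.2 labels that administration as baseline and the later ones as ongoing, and a sensible analyst would use a rating made after exposure. Similarly, section 6.1 speaks of parents here and of enrolled parents elsewhere. A responder denominator is the natural reading, because completeness has its own goal: "Percentage of enrolled parents who complete data collection, including interviews". Both are matters of missing detail.

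**Conclusion.** The inconsistency is real and limited. Section 4.4 drops the two acceptability and feasibility instruments from an assessment that replaces one containing them, and no reason is given. Transferred families who stay in the study would have no end-of-hospital AIM/FIM rating.

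If 10% to 20% of dyads are transferred, which is an assumption, 3 to 6 of 30 lack that rating (4 to 8 of 40). The all-enrolled discharge percentage is then undetermined over 10 to 20 points. At 30 dyads this can decide whether 70% is reached only if the observed discharge result is about 67% to 74% with 3 missing, or about 63% to 83% with 6 missing. The first follow-up and 12-month results are untouched.

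It would go too far to say that the feasibility conclusions of the study are compromised. Section 6.1 rules out hypothesis tests, the early-stopping criteria in section 8 do not mention acceptability, and none of the six parameters P1 to P6 in section 2.1 uses AIM or FIM. The change is worth making because it is cheap and because a rating not taken at transfer cannot be taken at that moment later.

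**What to change.** In section 4.4, add AIM and FIM to the measures completed at transfer, so that the list matches the discharge visit in section 4.2 and Table 1. If the omission is deliberate, say so and give the reason.

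As a minor clarification in section 6.1, name the post-exposure administration on which the 70% goal is judged (discharge or transfer, first follow-up, or 12 months, at the sponsor's choice) and report the number of missing ratings beside the percentage. Section 6.3 already provides for confidence intervals.

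The cost is 21 items (12 for AIM and 9 for FIM, as the protocol describes them) at a contact where four questionnaires are already given, plus a sentence or two in section 6.1. No visit is added. The extra burden is small but not nil: section 1.3 lists inconvenience or stress from completing questionnaires among the risks to parents.

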### **2.1 Primary Objective**

To conduct a pilot study to demonstrate TEMPO's feasibility as assessed by:

P1 In the target population, the % of eligible dyads who would consent to enroll (goal  $\geq 55\%$ )  
P2 In the target population, the % of enrolled dyads who would consent to randomization (goal  $\geq 70\%$ )  
P3 In the target population, the % of enrolled dyads who would complete all protocol components (goal  $\geq 70\%$ )  
P4 In the target population, the % of enrolled dyads who would participate for the full 12 months (goal  $\geq 70\%$ )  
P5 In the target population, the % of enrolled dyads who would provide complete data collection and interviews (goal  $\geq 70\%$ )

70%) and weekly and bi-weekly reporting of physical therapy interventions (goal  $\geq 50\%$ )  
P6 In the target population, the % of enrolled dyads who would perform physical therapy interventions at least 2-3x/week (goal  $\geq 70\%$ )

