- **Bi-weekly emails:** The PT will continue to send bi-weekly emails with developmental play activity and massage reminders until the 12 month follow-up appointment.
- **12 Month Follow-up Appointment:** At the standard of care 12 month follow-up appointment with the multidisciplinary neonatology team, the PT will administer a standardized assessment of gross and fine motor skills (Bayley Scales of Infant Development 3).

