#### Halting Rules

An infant may no longer participate in the study under any of the following circumstances:

- The medical condition of the infant deteriorates and the medical team no longer recommends PT or massage
- The infant experiences a severe AE or SAE related to the intervention
- The Parent is no longer interested in participating

In the event that an infant has an AE related to massage medium (Aquaphor), then massage will be performed without the medium or with a medium approved by the medical team once the skin has healed.

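### Sections 4.4 and 8 do not separate stopping TEMPO from leaving the study, so read as written a medical stop also ends later outcome and event follow-up

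*Combined protocol and SAP*

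**What the plan says.** Section 4.4 introduces its list with "An infant may no longer participate in the study under any of the following circumstances". The first item is "The medical condition of the infant deteriorates and the medical team no longer recommends PT or massage". The second, repeated in Section 8 under Halting Rules, is "The infant experiences a severe AE or SAE related to the intervention". The third is parental loss of interest. All three sit under one stem, and that stem concerns the study rather than the intervention.

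On data after an exit, Section 4.4 says only "If the parent chooses to withdraw their infant for any reason, the parent does not have to complete the above measures". It is silent on measures after a medical stop. For an infant transferred to another hospital, it brings the discharge questionnaires forward instead of dropping them.

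Section 2.1 defines the retention parameter as "P4 In the target population, the % of enrolled dyads who would participate for the full 12 months", with a 70% goal. Section 6.1 analyses it as "Percentage of enrolled parents who are retained in the study at 12 months", and adds "reasons for attrition for those who do not complete the protocol". Sections 6.2 and 6.3 plan means, SDs, correlations and confidence intervals to size a later trial. They give no analysis set and no method for missing data.

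The later visits do not depend on TEMPO. Section 7 places the BSID-III "At the standard of care 12 month follow-up appointment with the multidisciplinary neonatology team" and also describes the 2-month appointment as standard of care.

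**The concern.** An infant can stop receiving massage and PT and still be followed. The plan has no such state. If the text is followed literally, a medical stop is also an exit, and the dyads affected are selected by the infant's condition or by harm from the intervention. Three things are at stake.

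- **Aim 3.** Scores due after the stop are missing for a reason plausibly related to those scores.
- **Safety.** Section 8 ties an adverse event to time in the study or use of the intervention. An infant who has left both arguably falls outside it, just when the outcome of a related serious event matters. Section 8 sets reporting times but no follow-up to outcome.
- **Feasibility parameters.** P4 counts a medical stop as non-retention. Willingness to be randomized is asked only in interviews at the two follow-up visits, so a dyad removed earlier cannot answer but remains among the enrolled.

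**Working it through.** **Which measures are exposed** (Table 1; Sections 1.4, 4.2, 4.3 and 5)

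- Not exposed: baseline questionnaires; infant and parent cortisol, if the stop follows the first massage session.
- Exposed: questionnaires at discharge and afterwards, CTS, both interviews, PAQ and BSID-III (the last two at 12 months only), and serial correlations that use these points.

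**Inputs.** The plan's 30 dyads reproduces closely: 0.55 × 57 = 31.35. There is no power calculation to check, because no hypothesis tests are planned. The documents give neither the share stopped for medical reasons (m) nor how far those infants or parents differ from the rest (d, in SDs). Both are assumptions here: m = 10% to 20% (3 to 6 of 30) and d = 0.5 to 1.

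**Aim 3 illustration.** Take two groups with the same within-group SD, the leavers d SDs worse. Using stayers only:

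- shift in mean = m × d (within-group SDs);
- full variance ÷ stayers' variance = 1 + m(1 − m)d²;
- stayers' SD ÷ full SD = 1 ÷ √(1 + m(1 − m)d²).

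| m | d | Mean shift | Variance ratio | SD ratio | SD too small by |
|---|---|---|---|---|---|
| 10% | 0.5 | 0.05 | 1.0225 | 0.989 | 1.1% |
| 10% | 1 | 0.10 | 1.09 | 0.958 | 4.2% |
| 20% | 0.5 | 0.10 | 1.04 | 0.981 | 1.9% |
| 20% | 1 | 0.20 | 1.16 | 0.928 | 7.2% |

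Sample size for a difference in means goes with the variance, so one built on the stayers' SD would need about 2% to 16% more.

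The shift is toward the healthier side, which is not the same numerical direction for every scale. Section 1.4 says higher CTS scores mean more difficult temperament, so a CTS mean would be too low. PSOC runs the other way (higher means greater self-efficacy), so its mean would be too high.

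**P4 illustration.** The 70% goal is 21 of 30.

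- With 3 medical stops, the others must reach 21/27 = 78%; with 6, 21/24 = 88%.
- If retention apart from medical stops were 80%, P4 = 0.80 × (1 − m): 72% at m = 10% and 64% at m = 20%. It falls to 70% at m = 1 − 0.70/0.80 = 12.5%.

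**The case against.** The strongest reply is that exit is inferred. The stem uses 'may', whereas Section 5.1 says a session, and Section 8 the study, will be stopped. The waiver of parent measures covers parental withdrawal only. This has force: a reader might infer that the protocol forbids collecting outcomes after a medical stop, and it never says so. But the same stem governs loss of parental interest, which plainly ends participation, and it recurs under Halting Rules. If 'may' is discretionary, the plan gives no criterion for who is followed. Either reading needs the same clarification.

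A reader might also infer that the sickest infants leave as a class. The text is narrower. Deterioration counts only when the medical team also no longer recommends PT or massage. Both sections let massage continue after a reaction to the medium. Section 3.1 places referral at clinical stability, and Section 8 calls reported massage AEs rare, though less studied below 28 weeks.

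On P4, reasons for attrition are to be reported, and Section 9 puts reasons for dropout in the Annual Report, so medical stops can be separated descriptively. Attrition from all causes is a legitimate planning quantity. A reader might conclude that P4 is wrongly defined and should mean still in follow-up; that would be a preference for another estimand, not an error. These reports do not, however, recover missing scores, interviews or event outcomes.

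On size, with 24 dyads observed a 95% interval is about ±0.42 SD for a mean (2.069/√24) and about −22% to +40% for an SD. The illustrated bias lies inside both. That limits its importance, but those intervals do not allow for selective loss.

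On safety, AEs reach the independent monitor within 24 hours, and related unexpected serious events are reported within 3 or 7 days. What is missing is explicit follow-up to outcome.

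**Conclusion.** The point holds as a gap in the withdrawal rules. Stopping TEMPO and leaving the study are not separated, and no follow-up is provided after a medical stop. Read as written, the affected dyads lose all measures due after the stop and follow-up of the event's outcome.

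Bias in Aim 3 is a plausible risk, not an established effect. Its size depends on a discontinuation rate and an outcome difference that the documents do not give. The figures of 0.05 to 0.20 SD for means and about 1% to 7% for SDs hold only for m = 10% to 20%, d = 0.5 to 1, and equal spread in both groups. Fewer stops or a smaller difference would make them negligible. The case for acting rests on how cheaply the loss can be avoided at visits that take place anyway.

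**What to change.** Leave the stopping events exactly as they are. Then:

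1. In Section 4.4 and in the Halting Rules, define two states: 'TEMPO stopped' and 'withdrawn from study'.
2. State that, unless the parent withdraws, a dyad with TEMPO stopped continues AE follow-up, including the outcome of the event that led to the stop. The applicable parent and infant measures are still collected at the standard-of-care first and 12-month corrected-age visits. List which apply: AIM, FIM and the acceptability interview mean less for a family no longer receiving TEMPO.
3. Keep P4 as defined over all enrolled dyads, and also report it split by medical stop, death and parent withdrawal.

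The cost is a short amendment with matching consent wording, plus some questionnaire burden for a few families. The visits are routine but the questionnaires and interviews are research procedures, and these families may decline them.
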